#### 6.4. Electrocardiogram

Twelve-lead ECGs will be recorded in a supine position so that the different ECG intervals (RR, PR, QRS, QT) can be measured. ECGs will be assessed at screening, Baseline, and Week 6. The ECGs will be read by a central reader. The ECG variables that will be analyzed are heart rate, PR interval, RR interval, QRS interval, QT interval, and QTc using the following correction methods: Bazett's formula (QTcB) and Fridericia's formula (QTcF).

Bazett's formula:  $QTcB (msec) = QT (msec) * (HR(bpm)/60)^{0.5};$ 

Fridericia's formula:  $QTcF (msec) = QT (msec) * (HR(bpm)/60)^{0.33}$ 

Descriptive statistics for observed values and changes from average predose will be presented by treatment group for the above ECG variables at each scheduled time point. Average predose ECG is defined as the average of all ECG results collected up to and including the day of the first dose of study drug.

The identification of treatment-emergent abnormal ECG values is based on the post-baseline value (a value occurring after the first study drug administration) being out of range while the average predose value is either missing or within the limits given in **Error! Reference source not found.** If post-baseline ECG results are above the upper limits (abnormally high) and the average predose value is below the lower limits (abnormally low), then the post-baseline abnormality will also be considered treatment-emergent. The same applies to the post-baseline value being below the lower limits (abnormally low) with the average predose value being above the upper limits (abnormally high). The number and percentage of subjects with treatment-

emergent ECG values outside the pre-defined normal limits defined below will be presented for the postbaseline value by treatment group.

	Outside of normal limit if	
ECG Parameter	Abnormally low	Abnormally high
Heart Rate (bpm)	$\leq$ 50 bpm	≥100 bpm
PR interval (msec)	$\leq 120$ msec	$\geq$ 200 msec
QRS interval (msec)	$\leq 60$ msec	≥120 msec
QT interval (msec)	$\leq 200$ msec	≥500 msec

**Table 7: Abnormal Limits for ECG Parameters** 

In addition, the number and percentage of subjects within each of the categories defined below will be presented for the average predose and the maximum postbaseline value during the DB phase by treatment group. The maximum postbaseline value during the double-blind period will be computed for each ECG parameter using data from both scheduled and unscheduled visits.

Categories to assess QT prolongation:

QTc Interval:

- Normal QTc ( $\leq$ 450 msec for male and  $\leq$ 470 msec for female)
- QTc (>450 to  $\leq$ 480 msec for male and >470 to  $\leq$ 480 msec for female)
- QTc (>480 to  $\leq$ 500 msec)
- QTc (>500 msec)

Clinically significant QTc:

- No (≤500 msec)
- Yes (>500 msec)

Change from baseline:

- No concern:  $QTc \leq 30$  msec
- Concern: QTc > 30 60 msec
- Clear concern: QTc >60 msec

The interpretation of the ECGs as determined by the central reader will be displayed by the number of subjects and percentages meeting the normality criteria. The interpretation will be summarized over time.

Listings of treatment-emergent abnormal ECG values, QTc intervals >450 msec for male and >470 msec for female, and QTc interval changes >30 msec will also be provided.

#### 6.5. Other Safety Parameters

## 6.5.1. Columbia Suicide Severity Rating Scale (C-SSRS)

Emergence of suicidal ideation will be assessed using the C-SSRS. The C-SSRS is a low-burden measure of the spectrum of suicidal ideation and behavior. It is a semi-structured clinician-administered questionnaire designed to solicit the occurrence, severity, and frequency of suicide-related ideation and behaviors during the assessment period.

Using the C-SSRS, potentially suicide-related events will be categorized using the following scores:

#### Suicidal Ideation (1-5)

- 1: Wish to be Dead
- 2: Non-specific Active Suicidal Thoughts
- 3: Active Suicidal Ideation with Any Methods (Not Plan) without Intent to Act
- 4: Active Suicidal Ideation with Some Intent to Act, without Specific Plan
- 5: Active Suicidal Ideation with Specific Plan and Intent

#### Suicidal Behavior (6-10)

- 6: Preparatory Acts or Behavior
- 7: Aborted Attempt
- 8: Interrupted Attempt
- 9: Actual Attempt (non-fatal)
- 10: Completed Suicide

If no events qualify for a score of 1 to 10, a score of 0 will be assigned (0="no event that can be assessed on the basis of C-SSRS"). Higher scores indicate greater severity.

A frequency distribution at each time point by treatment group will be provided. Shifts from baseline to the maximum postbaseline score during the double-blind phase will be summarized by treatment group.

The maximum postbaseline score during the double-blind phase assigned for each subject will be summarized into one of three broad categories: No suicidal ideation or behavior (0), Suicidal ideation (1-5), Suicidal behavior (6-10). Shifts from baseline to the maximum category during the double-blind phase will be summarized by treatment group.

In addition, a frequency distribution at each time point for whether the "subject has engaged in non-suicidal self-injurious behavior" will be presented by treatment group.

A listing of C-SSRS items throughout the study for subjects with Suicidal Ideation or Behavior at any time point will be provided.

## 6.5.2. Physicians Withdrawal Checklist (PWC)

The Physician Withdrawal Checklist (20 items; PWC-20) is a simple and accurate method used to assess potential withdrawal symptoms following cessation of treatment and will be measured on Week 6, during the telephone contact, and at the follow-up visit. Each of the 20 items is rated on a 4-point Likert scale, with 0=not present, 1=mild, 2=moderate, 3=severe.

For each of the 20 items, a frequency distribution will be provided by treatment group at each time point.

In addition, symptoms at follow-up (telephone contact and the follow-up visit) will be compared to the Week 6/early withdrawal visit and will be summarized as follows: new or worsened symptoms, symptoms present and unchanged, improved symptoms, and no symptoms. This analysis will be repeated including only subjects whose Week 6/early withdrawal visit is the day after their last dose of study drug.

A total score (0 to 24) will be calculated by adding the scores of the following 8 items: Nausea-Vomiting, Diarrhea, Poor Coordination, Diaphoresis, Tremor-Tremulousness, Dizziness-Lightheadedness, Increased Acuity Sound Smell Touch, Paresthesias. If 1 or more items are missing, the total score will be left missing. Higher scores represent a more severe condition. The total score will be summarized with descriptive statistics by treatment group.

A listing of subjects with withdrawal symptoms following abrupt cessation of treatment (i.e., those subjects with new or worsened symptoms compared to the Week 6/early withdrawal visit) will be presented.

## 6.5.3. Arizona Sexual Experiences Scale (ASEX)

Effect on sexual functioning will be assessed using the ASEX at Baseline and Week 6. The ASEX is a five-item rating scale that quantifies sex drive, arousal, vaginal lubrication/penile erection, ability to reach orgasm, and satisfaction from orgasm. Each of the 5 items is rated on a 6-point Likert scale, ranging from 1 to 6. The 5 items are summed to create a total score, ranging from 5 to 30, with the higher scores indicating more sexual dysfunction. If any item of the scale is missing at a visit, the total score for that scale at that visit will be left blank.

For each of the 5 items, a frequency distribution will be provided by treatment group and gender at each time point. In addition, for each of the 5 items, a frequency distribution will be provided by treatment group, combining the responses for the genders. For this analysis, "vaginal lubrication/penile erection" will be summarized as 1 question. The ASEX total score at each time point and the change from baseline will be summarized with descriptive statistics by treatment group.

The number and percentage of subjects who have ASEX total score 19 or greater, or a score of 5 or greater on any item, or a score of 4 or greater on any 3 items, reflecting sexual dysfunction, will be summarized at each time point by treatment group.

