1.3. Overall Risk and Benefit Assessment

As further described in Section 1 and the rationale for this study (Section 1.2), MDD is a common, serious, recurrent mental disorder. MDD is the leading cause of disability, and its prevalence is rising.⁶³

Current therapies commonly used as first-line ADT in patients with MDD (eg, SSRIs and SNRIs) are sub-optimally effective in some patients who require adjunctive treatment, or who are otherwise poorly compliant because of their associated adverse events, such as weight gain and sexual side effects. Currently approved adjunctive treatments are limited to the atypical antipsychotic drug class, which also present considerable tolerability concerns (eg, metabolic syndrome, akathisia, and extrapyramidal symptoms [EPS]). The orexin-receptor antagonist class offers a novel mechanism of action that may prove to be a valuable alternative in the adjunctive treatment of MDD, but without the side effects observed with other medications commonly used in this setting such as weight gain, sexual side effects, akathisia, or EPS. The preliminary data regarding effects on cortisol and stress-response suggest that JNJ-42847922 may have clear advantages over the standard of care in patients with certain co-morbid medical conditions typically associated with dysregulation of the HPA axis.

The currently available data (see Section 1.1.2, Clinical Studies, and the JNJ-42847922 Investigator's Brochure²²) support this clinical study that investigates the efficacy and safety of JNJ-42847922 in adult subjects with MDD who have responded inadequately to commonly used ADTs.

The antidepressant effect of JNJ-42847922 was clinically relevant as early as Day 11 of exposure and was sustained at least 14 days after treatment discontinuation. The effect of JNJ-42847922 was largely related to an effect on the core symptoms of depression, and overall unrelated to its effect on sleep related events.

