
Arizona Sexual Experiences Scale (ASEX)

Results from the ASEX will be tabulated by treatment.

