#### 6.2. Clinical Laboratory Tests

Descriptive statistics will be presented for all chemistry (including the lipid panel), hematology (including hemoglobin A1c [HbA1c]), and urinalysis (pH and specific gravity) laboratory parameters at each scheduled time point. In addition, change from baseline to all postbaseline time points will be summarized for chemistry, hematology, and urinalysis (pH and specific gravity) parameters and displayed by treatment group.

The number and percentage of subjects with treatment-emergent postbaseline markedly abnormal postbaseline values will be presented by treatment group. Clinical laboratory test values will be considered "treatment-emergent markedly abnormal" (TEMA) using the criteria defined by the sponsor listed in Attachment 3. The identification of TEMA laboratory values is based on the postbaseline value being out of range while the baseline value is either missing or within the range given in Attachment 3. If postbaseline laboratory results are above the upper limit and the baseline value is below the lower limit, then the postbaseline abnormality will also be considered TEMA. The same applies to the postbaseline value being below the lower limit with the baseline value being above the upper limit.

In addition, the number of subjects with the following shifts in chemistry laboratory values from baseline to the maximum postbaseline time point will be presented:

- Glucose:
  - from <100 mg/dL to  $\geq 126 \text{ mg/dL}$  (normal to high)
  - from <100 mg/dL to  $\geq 100 \text{ mg/dL} <126 \text{ mg/dL}$  (normal to borderline high)
  - from [ $\geq 100 \text{ mg/dL} \langle 126 \text{ mg/dL} \rangle$ ] to  $\geq 126 \text{ mg/dL}$  (borderline high to high)
- Triglycerides:
  - $\circ$  from <150 mg/dL to  $\geq$ 200 mg/dL (normal to high/very high)
  - o from <150 mg/dL to  $\geq 500 \text{ mg/dL}$  (normal to very high)
  - $\circ~$  from [ $\geq \! 150~mg/dL$   $<\!\! 200~mg/dL$ ] to  $\geq \! 200~mg/dL$  (borderline high to high/very high)
  - o from [ $\geq$ 150 mg/dL <200 mg/dL] to  $\geq$ 500 mg/dL (borderline high to very high)
  - o from [ $\geq 200 \text{ mg/dL} \langle 500 \text{ mg/dL} \rangle$ ] to  $\geq 500 \text{ mg/dL}$  (high to very high)
- Total Cholesterol

- $\circ$  from <200 mg/dL to  $\geq$ 200 mg/dL (normal to borderline high/high)
- $\circ$  from <200 mg/dL to  $\geq$ 240 mg/dL (normal to high)
- $\circ$  from <200 mg/dL to [ $\geq$ 200 mg/dL <240 mg/dL] (normal to borderline high)

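### ASEX sexual dysfunction is tabulated only as prevalence at Baseline and Week 6, so new onset on study drug cannot be separated from persistence or recovery

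*SAP*

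**What the plan says.** SAP 6.5.3 sets the schedule: "Effect on sexual functioning will be assessed using the ASEX at Baseline and Week 6". It then plans these outputs:

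- item frequencies by arm and gender at each time point, and again with the genders combined;
- a continuous summary: "The ASEX total score at each time point and the change from baseline will be summarized with descriptive statistics by treatment group";
- a binary count: "The number and percentage of subjects who have ASEX total score 19 or greater, or a score of 5 or greater on any item", or at least three items scored 4 or more, "reflecting sexual dysfunction, will be summarized at each time point by treatment group".

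The binary count carries no condition on baseline status, and no shift table or listing goes with it. Protocol 11.7 adds only this: "Results from the ASEX will be tabulated by treatment".

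ASEX is among the endpoints of the primary safety objective (Protocol 2.1, SAP 1.1). Inclusion criterion 4 requires at least 4 weeks of an SSRI/SNRI at a stable dose by screening, and Protocol section 6 has subjects continue it unchanged.

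**The concern.** A safety reader will want to know how many subjects without sexual dysfunction at entry developed it on study drug. Two prevalence columns do not answer that. The protocol itself gives reason to expect positives at baseline. Section 1.3 names sexual side effects among the problems of first-line antidepressants, and Attachment 2 lists sexual difficulties as events anticipated from the disease or the background regimen.

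The answer also bears on a stated hope for the drug. Protocol 1.3 suggests that the class may avoid the side effects of other treatments used in this setting, "such as weight gain, sexual side effects, akathisia, or EPS". If improving depression resolves some dysfunction while the drug starts some, the two flows offset each other in the Week 6 prevalence. They offset each other in the mean change as well.

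The SAP conditions on baseline in several neighbouring outputs:

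- In 6.2, a laboratory value is treatment-emergent when it is out of range after baseline "while the baseline value is either missing or within the range given in Attachment 3".
- In 6.4, an ECG value is treatment-emergent on "being out of range while the average predose value is either missing or within the limits".
- In 6.3, orthostatic hypotension is counted only if absent at baseline.
- In 6.5.1, C-SSRS scores and categories are shown as shifts.
- In 6.5.2, PWC symptoms at follow-up are classed as new or worsened, unchanged, improved or absent, relative to the Week 6/early withdrawal visit.

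**Working it through.** The plan states no figure on this point, so there is none to reproduce. The documents give no ASEX prevalence, onset or resolution rate. Every rate below is an assumption, with baseline prevalence varied from 30% to 70%.

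**What the two prevalences determine.** Let b be the proportion meeting the definition at baseline and w the proportion at Week 6, in the same subjects. New onset as a share of all subjects lies between max(0, w - b) and min(w, 1 - b). Dividing by 1 - b gives the rate among subjects free of dysfunction at baseline.

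| b | w | New onset, share of all | New onset among those free at baseline |
|---|---|---|---|
| 30% | 30% | 0 to 30% | 0 to 43% |
| 50% | 50% | 0 to 50% | 0 to 100% |
| 50% | 60% | 10 to 50% | 20 to 100% |
| 70% | 70% | 0 to 30% | 0 to 100% |

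An unchanged prevalence therefore fits no new cases at all, or many new cases offset by recoveries.

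**How far the net difference can depart from the onset difference.** Week 6 prevalence = b × (1 - resolution) + (1 - b) × onset. Assume onset 15% on drug and 5% on placebo, and resolution 20% on drug and 10% on placebo.

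- b = 50%: drug 0.5 × 0.80 + 0.5 × 0.15 = 47.5%; placebo 0.5 × 0.90 + 0.5 × 0.05 = 47.5%; difference 0.
- b = 30%: drug 0.3 × 0.80 + 0.7 × 0.15 = 34.5%; placebo 0.3 × 0.90 + 0.7 × 0.05 = 30.5%; difference +4 points.
- b = 70%: drug 0.7 × 0.80 + 0.3 × 0.15 = 60.5%; placebo 0.7 × 0.90 + 0.3 × 0.05 = 64.5%; difference -4 points.

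The onset difference among those at risk is 10 points in all three cases.

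**Without any difference in recovery.** Assume onset 25% on drug and 10% on placebo, with resolution 10% in both arms. The resolution terms cancel, so the prevalence difference is (1 - b) × 15 points: 10.5 at b = 30%, 7.5 at b = 50% and 4.5 at b = 70%. Here the signal is diluted but keeps its direction.

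**The dysfunction definition.** With no item at 5 or more and fewer than three items at 4 or more, the largest possible total is 4 + 4 + 3 + 3 + 3 = 17. Any total of 19 or more therefore already meets an item criterion, so the total-score criterion adds no subject.

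**The case against.** The strongest reply is that the comparison between arms is already sound. Assignment is randomized, every arm continues the background antidepressant, baseline prevalence is tabulated beside Week 6, and the total score has a change from baseline. New sexual complaints are also summarized as TEAEs by preferred term and arm (SAP 6.1), and Protocol 11.7 includes worsening of pre-existing conditions. All of this stands. A reader might infer that the background SSRI/SNRI confounds the drug-placebo contrast, or that ASEX has no baseline reference. The documents support neither reading. What these outputs do not supply is the split of the net ASEX change into onset and recovery; TEAEs come from adverse event reporting, not from the scale chosen for this purpose.

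A reader might also take ASEX to be the only thresholded safety count in the SAP without a baseline condition. It is not. The absolute QTc categories in SAP 6.4 are tabulated for the average predose and the maximum postbaseline value without cross-classification, with change categories alongside. The SAP uses both formats, so the argument rests on what the table can show, not on inconsistency.

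Finally, because 6.5.3 leaves the total blank when any item is missing, one might infer that such subjects drop out of the positive count through the total-score criterion. That criterion is redundant with the item criteria, so a blank total by itself cannot change the flag.

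The numerical example is constructed. Exact cancellation needs higher onset and higher recovery on drug together, at one particular baseline prevalence.

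**Conclusion.** The point holds in a limited form. The planned prevalence table gives a valid net comparison with placebo, but it does not identify new-onset dysfunction in a population expected to include baseline positives. Under the assumed rates, a threefold difference in onset appears as anything from -4 to +4 points as baseline prevalence moves from 70% to 30%, and as zero at 50%. These figures show what the table could hide; they do not predict what the trial will find.

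The consequence is modest. The table is descriptive and untested, in a study that Protocol 11.8 describes as not confirmatory. Baseline and Week 6 values are both collected, so nothing is lost irrecoverably, and the primary efficacy analysis is unaffected. The change is worth making because ASEX serves the primary safety objective and the missing output is cheap to produce.

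**What to change.** Add two outputs to SAP 6.5.3:

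- a shift table of the dysfunction flag from baseline to Day 42/End point (DB) by arm (No to Yes, Yes to No, unchanged), in subjects with both assessments;
- treatment-emergent sexual dysfunction by arm, as n/N among subjects who did not meet the definition at baseline.

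Keep the planned prevalence and change-from-baseline summaries, which carry the net comparison. No new data are needed: the schedule has ASEX at Day 1 and at the end-of-treatment/early withdrawal visit, and the Day 42 window for ASEX in SAP Table 1 runs from Day 2 to the end of the double-blind phase.

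The cost is a few lines of SAP text and a small amount of programming. The downside is a smaller denominator for the incidence: if baseline prevalence were 30%, 50% or 70%, the at-risk group would be 70%, 50% or 30% of subjects with both assessments. The estimate will be less precise, and N should be shown with it.

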# 7. SUMMARY OF PLASMA CONCENTRATIONS FOR JNJ-42847922, M12, AND M16

Plasma concentrations for JNJ-42847922 and metabolites (M12 and M16) will be summarized by dose, day and time point, using descriptive statistics.

#### 8. BIOMARKERS

Details of the biomarker analyses are provided in a separate document.

#### ATTACHMENTS

#### Attachment 1: Conversion of Raw Score to T-Score for PROMIS-SD

Sleep Disturbance 8a				
Short Form Conversion Table				
Raw				
Score	T-Score	SE*		
8	28.9	4.8		
9	33.1	3.7		
10	35.9	3.3		
11	38.0	3.0		
12	39.8	2.9		
13	41.4	2.8		
14	42.9	2.7		
15	44.2	2.7		
16	45.5	2.6		
17	46.7	2.6		
18	47.9	2.6		
19	49.0	2.6		
20	50.1	2.5		
21	51.2	2.5		
22	52.2	2.5		
23	53.3	2.5		
24	54.3	2.5		
25	55.3	2.5		
26	56.3	2.5		
27	57.3	2.5		
28	58.3	2.5		
29	59.4	2.5		
30	60.4	2.5		
31	61.5	2.5		
32	62.6	2.5		
33	63.7	2.6		
34	64.8	2.6		
35	66.1	2.7		
36	67.5	2.8		
37	69.0	3.0		
38	70.8	3.2		
39	73.0	3.5		
40	76.5	4.4		

\*SE= Standard Error on T-score metric Adult version

#### Attachment 2: Conversion of Raw Score to T-Score for PROMIS-Fatigue

Fatigue 8a				
Short Form Conversion Table				
Raw Score	T-score	SE*		
8	33.1	4.8		
9	38.5	2.7		
10	41.0	2.2		
11	42.8	2.0		
12	44.3	1.9		
13	45.6	1.8		
14	46.9	1.8		
15	48.1	1.8		
16	49.2	1.8		
17	50.4	1.8		
18	51.5	1.7		
19	52.5	1.7		
20	53.6	1.7		
21	54.6	1.7		
22	55.6	1.7		
23	56.6	1.7		
24	57.5	1.7		
25	58.5	1.7		
26	59.4	1.7		
27	60.4	1.7		
28	61.3	1.7		
29	62.3	1.7		
30	63.3	1.7		
31	64.3	1.7		
32	65.3	1.7		
33	66.4	1.7		
34	67.5	1.7		
35	68.6	1.7		
36	69.8	1.8		
37	71.0	1.8		
38	72.4	2.0		
39	74.2	2.4		
40	77.8	3.7		

\*SE = Standard Error

	Markedly Abnormal Limits	
Laboratory Parameter (unit)	Low	High
Clinical Chemistry		
Albumin $(g/dL)$ but SI unit = $g/L$	2.4→24	6.0 →60
Alkaline phosphatase (U/L)	N/A	250
Alanine transaminase (SGPT) (U/L)	N/A	200
Aspartate transaminase (SGOT) (U/L)	N/A	250
Bicarbonate (mEq/L) but SI unit=mmol/L	15.1→15.1	34.9→34.9
Bilirubin (direct) (mg/dL) but SI unit = $\mu$ mol/L	N/A	$3.0 \text{ mg/dL} \rightarrow 51.3 \text{ umol/L}$
Bilirubin (total) (mg/dL) but SI unit = $\mu$ mol/L	N/A	$3.0 \text{ mg/dL} \rightarrow 51.3 \text{ umol/L}$
Blood urea nitrogen (mg/dL) but SI unit=mmol/L	N/A	$50 \text{ mg/dL} \rightarrow 17.9 \text{ mmol/L}$
Calcium (mg/dL) but SI unit= $mmol/L$	$6 \rightarrow 1.497 \text{ mmol/L}$	$12 \rightarrow 2.994 \text{ mmol/L}$
Chloride (mEq/L or mmol/L)	94	112
Cholesterol ( $mg/dL$ ) but SI unit=mmol/L	N/A	$300 \rightarrow 7.758 \text{ mmol/L}$
Creating kinase (U/L)	N/A	990
Creatining $(mg/dL)$ SL unit=umol/L	N/A	$3 \rightarrow 265.2  \mu\text{mol/I}$
Gamma glutamyl transferase (U/L)	N/A	300 U/I
Glucose Plasma (mg/dL) but SL unit=mmol/L	$40 \rightarrow 2.204 \text{ mmol/I}$	$300 \rightarrow 16.653 \text{ mmol/I}$
High-density linoprotein cholesterol (HDL) (mg/dL)	$35 \rightarrow 0.905$	500 7 10:055 mm0/L N/Δ
but SI unit=mmol/L	55 70.905	1V/ $A$
Lactic acid dehydrogenase (LDH) (U/L)	N/A	500
Low-density lipoprotein cholesterol (LDL) (mg/dL)	89→ 2.3015	160 → 4.1376 mmol/L
but SI unit=mmol/L		
Phosphate (mg/dL) but SI unit=mmol/L	2.2 → 0.71038 mmol/L	8.1→ 2.61549 mmol/L
Potassium (mmol/L)	3.0	5.8
Sodium (mEq/L) but SI unit = $mmol/L$	125→125	155→155
Total protein (g/L)	50	N/A
Triglycerides (mg/dL) but SI unit=mmol/L	N/A	500 → 5.645 mmol/L
Uric acid (mg/dL) but SI unit=µmol/L	1.5→89.22	10 → 594.8 µmol/L
Hematology		•
Hematocrit (%) – female	0.28	0.50
- male	0.24	0.55
Hemoglobin $(g/dL)$ but SI unit= $g/L$	8→80	19 → 190
Hemoglobin A1c (%)	4	8
Neutrophils (%)	30	90
Monocytes (%)	N/A	20
Eosinophils (%)	N/A	10
Basophils (%)	N/A	6
Lymphocytes (%)	10	60
Reticulocytes (%)	0.5	1.5
Platelet count $(10^9/L^2)$ giga/L)	100	600
Red blood cell (RBC) count $(10^{12}/L)$ tera/L) - female	3.0	5.5
- male	3.0	6.4
White blood cell (WBC) count $(10^9/L; giga/L)$	2.5	15.0
Urinalysis	2.0	10.0
Urine pH	N/A	6.5
Urine specific gravity	< 1.001	> 1.035

